## 1. BACKGROUND AND RATIONALE

### 1.1 BACKGROUND

ZX008 (fenfluramine hydrochloride) is under clinical development for the adjunctive treatment of patients with Dravet syndrome (DS).

Dravet syndrome, also known as severe myoclonic epilepsy of infancy (SMEI), is a rare and severe form of epilepsy first described by Charlotte Dravet in 1978 (Dravet 1978). The condition most commonly appears during the first year of life as frequent febrile seizures. As the condition progresses, other types of seizures typically occur, including myoclonic seizures and status epilepticus (Dravet 1978). Following the appearance of these seizures, affected children develop several co-morbid conditions including psychomotor regression, ataxia, sleep disturbance, and cognitive impairment. Intellectual impairment begins to become apparent around age 2 years due to lack of intellectual/behavioral progression. Dravet children often have a lack of coordination, poor development of language, hyperactivity, and difficulty relating to others (Dravet 1978; Hurst 1990). The degree of cognitive impairment appears to correlate, at least in part, with the frequency of seizures, and might be a result of repeated cerebral hypoxia. Children with DS also encounter a higher incidence of Sudden Unexpected Death in Epilepsy (SUDEP; Nashef 2012) than other populations with epilepsy. Indirect evidence has linked SUDEP to several possible etiologies, including seizure-induced apnea, pulmonary edema, dysregulation of cerebral circulation, and cardiac arrhythmias (Shorvon 2011), although the actual etiology remains unknown and other mechanisms have not been ruled out. The vast majority of patients who survive to adulthood are wholly dependent on around-the-clock caregivers and eventually live in institutional care homes.

Zogenix is conducting an international, multicenter, open-label, long-term safety study of ZX008 in pediatric and young adult subjects with Dravet syndrome who have successfully completed 14 weeks of treatment in core study ZX008-1501, ZX008-1502, and ZX008-1504 Cohort 2, or successfully completed core study ZX008-1504 Cohort 1, and are candidates for continuous treatment for an extended period of time. The ZX008-1503 trial will consist of a 12-month open-label extension (OLE) Treatment Period and a 2-week Post-Dosing Period. Thus, subjects who complete this trial will have been treated with ZX008 for a minimum of up to 1 year (including their participation in both the core study and this study).

### 1.2 RATIONALE FOR CURRENT SUB-STUDY, ZX008-1503-SS01

This is a sub-study to the ZX008-1503 OLE trial, which will include up to 20 participants who are enrolled in Study ZX008-1503. This is an exploratory sub-study to provide preliminary information on the overall usability and performance of the Empatica Embrace watch system (Embrace) in outpatients with Dravet syndrome.

Seizure frequency is the primary outcome measure for individual treatment and for clinical trials. The current gold standard for demonstrating efficacy of new anti-epileptic drugs is a 50% reduction in seizure frequency. This efficacy standard is based on patients or their caregivers maintaining seizure diaries.

Use of sensitive seizure detection technology may allow greater accuracy in seizure counting. Seizure detection technology may also provide means to address specific clinical questions, such as the occurrence of unwitnessed seizures during periods of sleep.

The Embrace has been designed for automated convulsive seizure detection and characterization. The Embrace watch monitors electrodermal activity (EDA) and accelerometer-sensed changes in motion to analyze the information and detect patterns that are typically observed in convulsive seizures in real-time. The data can then be used to compare seizure detections, false alarms, and seizures that are not detected, to e-diary seizure report information.

This sub-study for patients enrolled in the open-label extension study may provide insights into seizure triggers, such as temperature, or facilitate seizure counts during sleep and allow for comparison of various endpoints captured by the Embrace to the same endpoints captured in an electronic hand-held seizure diary.

## **2. STUDY OBJECTIVES AND ENDPOINTS**

### **2.1 PRIMARY OBJECTIVE**

The primary objective of the study is:

- To assess the overall usability and performance (correct use and ease of use) of the Empatica Embrace Seizure Detection watch system (Embrace) in outpatients with Dravet syndrome.

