### **4.1 INCLUSION CRITERIA**

In addition to meeting all of the main Study ZX008-1503 inclusion criteria subjects in the sub-study must also be willing to wear and use the Embrace watch and parents/caregivers must be willing to use the Alert app. This includes:

1. Subject is willing to wear the Embrace watch on the wrist (alternatively ankle, if needed for younger children). Subjects are asked to wear the watch for as many hours of the day as possible and for the entire night, if possible, for the duration of the sub-study.
2. Subject's parent/caregiver is willing to use the Alert App and receive voice and SMS notifications on their personal smart-phone, and ensure the smart-phone has internet connectivity; iOS 8.2 or higher is required for iPhone users.
3. Subject/subject's caregiver is willing to ensure that the Embrace watch remains within close proximity of the paired iPod Touch running the Empatica Alert app.
4. Subject/subject's caregiver is willing to ensure that the Embrace system is properly stored when not in use, and is not left exposed to direct sunlight, moisture, humidity or rain while in storage. The Embrace watch is water resistant but should never be submerged in water. Bathing and/or showering with the watch is acceptable, however.
5. Subject/subject's caregiver is willing to regularly clean the Embrace watch, routinely inspect the watch for sharp edges and damage, and ensure the watch is never worn over damaged or broken skin.
6. Subject/subject's caregiver is willing to ensure that the Embrace system is properly charged daily during a time when the subject is being observed so any seizures that occur during times that the device is not being worn are able to be added to the record manually.

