#### **8.3.2 Efficacy Analysis**

The primary criteria for evaluation in the sub-study is the change over time in the 5-point Likert Ease of Use Questionnaire to measure user experience.

Secondary exploratory efficacy criteria for evaluation include change over time in the following:

- Perceived Stress Scale (PSS) to measure caregiver burden.
- Correlation of monthly (28-day) convulsive seizure count between the Embrace watch and seizure diary.
- Size of EDA response during and in the post-ictal hour of convulsive seizures.
- Skin-surface temperature (measured on wrist).
- Frequency of fever-related convulsive seizures.
- Comparison of convulsive seizure count during periods of sleep, and during the combined titration and maintenance periods between the Embrace watch and seizure diary.
- Correlation of convulsive seizure time and classification as determined by Embrace watch and seizure diary.
- EQ-5D-5L to measure quality of life of the parent/caregiver quality of life while using the Embrace.
- HADS to measure affective symptoms of the parent/caregiver while using the Embrace.

All other efficacy criteria are identical to those in the main Study ZX008-1503.

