#### **8.4 STATISTICAL METHODS**

All safety data will be summarized as described in the main Study ZX008-1503 protocol and associated Statistical Analysis Plan. Efficacy analyses for sub-study participants that rely on the ERT seizure diary or are specific to the Embrace will not be included in the main Study ZX008-1503 analyses. Exploratory data for the Embrace watch system data will be processed as follows:

Continuous data will be summarized using descriptive statistics including means, standard deviations, medians, lower and upper quartiles, and ranges. Categorical variables will be summarized with frequencies and percentages. Confidence intervals will be calculated for key parameters or estimates as warranted.

A complete description of the statistical analyses and methods will be available in the Statistical Analysis Plan, which will be finalized before the database is locked.

The primary analysis will rely on descriptive statistics to summarize responses to the Ease of Use Questionnaire from each time point where the questionnaire is administered. In particular, the modal, ie, most frequent, response to each item on the questionnaire will be reported at each time point. Responses across all items on the questionnaire will be summed to create an overall index that will also be reported at each time point.

Exploratory data for the Embrace watch system data will be processed as follows:

- Embrace’s automated convulsive seizure detection results will be manually compared to the diary counts of convulsive seizures. Spearman rank correlation will be used to quantify agreement.
- The Spearman rank correlation described above will be repeated separately for events during periods of sleep and for events while awake, based on Embrace’s determination of sleep/wake (periods of sleep will be based on actigraphy and EDA as measured by the Embrace watch).

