## **9. DATA HANDLING PROCEDURES**

The investigator (or delegate) will maintain individual records for each subject. These records should include dates when a subject visited the study site, study-required information and data, and other notes as appropriate. These records constitute source data.

A CRF will be provided by the sponsor (or delegate) for each subject enrolled into the sub-study. Study site staff will enter data directly into the validated electronic data capture (EDC) system by completing the CRF via a secure internet connection. The investigator is

responsible for ensuring accurate and proper completion of the CRF for recording data according to the instructions given in the CRF.

All entries in the CRF must be backed up by the relevant source data at the study site. All source data will be kept according to all applicable regulatory requirements. Source data must be completed legibly for each subject enrolled into the sub-study and signed by the investigator (or delegate).

Data entry in the CRF must be completed in a timely manner so that they always reflect the latest observations on the subjects enrolled in the sub-study.

All Embrace data will be automatically captured and stored in a de-identified manner on a secure MySQL database and/or secured Amazon S3 buckets as part of the Empatica production server and analytics backend. Individual subjects will be tracked by the de-identified subject id assigned to each subject at the consent. No personally identifiable information will be directly linked to BPT data.

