## APPENDIX 1 – LIKERT EASE OF USE QUESTIONNAIRE

Over the last week, using the Embrace watch was:

- 1 – Very difficult
- 2 – Difficult
- 3 – Neutral
- 4 – Easy
- 5 – Very easy

Over the last week, using the Mate App was:

- 1 – Very difficult
- 2 – Difficult
- 3 – Neutral
- 4 – Easy
- 5 – Very easy

Over the last week, using the Alert App was:

- 1 – Very difficult
- 2 – Difficult
- 3 – Neutral
- 4 – Easy
- 5 – Very easy

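### The primary objective names correct use as well as ease of use, but no criterion, assessment or analysis in the document measures correct use

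*Combined protocol and SAP*

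**What the plan says.** The primary objective (Section 2.1, and the same in the Synopsis) is to assess the watch system's overall "usability and performance (correct use and ease of use"). The bracket names two components.

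Section 8.3.2 then gives one primary criterion: "The primary criteria for evaluation in the sub-study is the change over time in the 5-point Likert Ease of Use Questionnaire to measure user experience". Section 8.4 follows it: "The primary analysis will rely on descriptive statistics to summarize responses to the Ease of Use Questionnaire from each time point", by the modal response per item and a summed index. The three items in Appendix 1 share one form, for example "Over the last week, using the Embrace watch was", answered on a five-point scale of difficulty.

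What families are expected to do is set out in Section 4.1. On wear it says: "Subjects are asked to wear the watch for as many hours of the day as possible and for the entire night, if possible". It also covers keeping the watch near the paired iPod with the Alert app running, charging it daily, cleaning it and inspecting it. All of this is worded as willingness at entry.

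Section 8.2.2 runs the sub-study effectiveness analyses on the EmB Population, which requires at least one week of valid Embrace seizure data. 'Valid' is not defined. On device data, Section 9 states: "All Embrace data will be automatically captured and stored in a de-identified manner".

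**The concern.** This is a usability pilot. Whether families kept the watch on, charged and within range of the iPod is a different question from whether they found it easy. A caregiver can rate the watch very easy in a week when it was hardly worn, and another can rate it difficult while using it as instructed. If only the rating is reported, one named component of the primary objective has no result.

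There is also a knock-on effect. Section 8.4 compares device seizure counts with diary counts. Without a record of worn time, a seizure missed by the algorithm cannot be told apart from one that occurred while the watch was off. Daily charging guarantees some time off the wrist.

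**Working it through.** The plan has no figure to reproduce: the sample is up to 20 subjects, set on feasibility (Sections 3.2 and 8.1). The check is a trace of each component of the objective through the document, followed by some supporting arithmetic.

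**Trace**

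| Place | Ease of use | Correct use |
|---|---|---|
| Primary objective (2.1) | named | named |
| Primary criterion (8.3.2) | questionnaire | none |
| Secondary criteria (8.3.2) | not applicable | none |
| Schedule (Table 1, Section 5) | questionnaire visits | none |
| Instrument (Appendix 1) | three ease ratings | no item on wear, charging, proximity or app running |
| Analysis (Synopsis, 8.4) | mode per item, summed index | none |
| Entry criteria (4.1) | not applicable | willingness only |
| Population (8.2.2) | not applicable | one-week filter, not reported |

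**How much use the EmB rule demands**

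Inputs: 7 days (8.2.2); 12 weeks = 84 days, extendable to 24 weeks = 168 days (3.3).

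- 7/84 = 8.3%, so a subject can qualify with no valid data for up to about 92% of 12 weeks.
- 7/168 = 4.2%, so up to about 96% of 24 weeks.

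The rule therefore screens out only near-total non-users and says little about the use made by those who remain.

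**Why the denominator matters**

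Assume, for illustration, 12 correct users among 20 fitted, with k non-users falling outside EmB. The rate among all fitted subjects is 12/20 = 60%. Within EmB it is 12/(20 − k):

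- k = 2: 12/18 = 67%
- k = 4: 12/16 = 75%
- k = 6: 12/14 = 86%

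**Precision of an added criterion**

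Exact (Clopper-Pearson) 95% limits for x of n are the 0.025 quantile of Beta(x, n − x + 1) and the 0.975 quantile of Beta(x + 1, n − x). With n = 20:

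- x = 12: 60% (36.1% to 80.9%)
- x = 16: 80% (56.3% to 94.3%)

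The counts are assumptions, because the documents give no expected rate. The intervals show how precise the added measure would be, not how large the gap is.

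**The case against.** The strongest reply is that this is a small descriptive pilot, that Section 8.4 leaves complete methods to a Statistical Analysis Plan to be finalised before database lock, and that device data are used elsewhere, for example in the device-diary comparison and the daily skin temperature averages. The size and descriptive purpose of the study do excuse wide intervals. They do not excuse having no measure for a named part of the primary objective. A later SAP could supply one, but no separate SAP text is in the documents, and the protocol gives it no correct-use criterion to analyse. The device-diary comparison bears on detection, not on use.

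A reader might infer more than the text supports:

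- *That incorrect use is removed from the data.* Section 4.4 makes withdrawal for refusing instructions discretionary, requires the reason to be recorded on the CRF, and keeps data collected up to discontinuation.
- *That the questionnaire is analysed only in those who managed to use the watch.* The primary analysis paragraph names no population. The criterion's place under Efficacy Analysis suggests EmB, but this is not stated, and the one-week bar is low.
- *That wear and connection logs already exist.* Section 9 speaks of Embrace data in general, Section 6.2.2.1 of raw data, and Section 6.2.1 of EDA, skin temperature and motion. Wear and gaps would have to be derived from these signals.

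**Conclusion.** The concern holds in this form: correct use is named in the primary objective, and nothing in the document defines, collects or reports it as an outcome. This affects one of the two named components. The only use threshold is a filter at 8.3% of the 12-week period, resting on an undefined term. If EmB also governs the questionnaire, near-total non-users could drop out of the ease result as well; that part depends on an inference from where the criterion sits.

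It would go too far to say that the trial could show no use at all, since each EmB subject has at least a week of valid data, or that the question could never be answered from the data stored. The supportable statement is that the plan does not specify how it will be answered. The conclusion rests on the current protocol text and on the stored signals being sufficient to derive periods with valid recorded data.

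**What to change.** In Sections 8.3.2 and 8.4, add a descriptive correct-use criterion beside the questionnaire, derived from the stored Embrace signals:

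- Report hours with valid recorded data per day and per night, by week.
- Report the proportion of all subjects fitted at Visit 1 who meet a numeric threshold fixed before data review, with an exact 95% CI. Do not restrict this to EmB.
- Count a subject as a non-user from the date of stopping, and tabulate withdrawals for non-compliance from the CRF.
- Define 'valid' once and use the same definition in the EmB rule. State which population the questionnaire analysis uses.
- State the limit of the measure: it captures wear and data capture, not every element of correct use, and a gap may mean non-wear, charging or the iPod out of range.

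This is a cheap improvement. It needs no extra visits, subjects or questionnaires, but it does need a derivation rule, a prespecified threshold and one extra table.

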### **2.2 SECONDARY OBJECTIVES**

The secondary exploratory objectives of the study are:

- To compare objective convulsive seizure count, as captured by the Embrace, to convulsive seizure count captured manually in the electronic seizure diary.
- To compare objective convulsive seizure count during periods of sleep, as captured by the Embrace, to convulsive seizure count during periods of sleep captured manually in the electronic seizure diary.
- To examine if the size of the electrodermal activity (EDA) response during and after a convulsive seizure is reduced over time with ZX008 treatment.
- To examine if skin-surface temperature changes with ZX008 treatment.
- To examine if skin-surface temperature levels are different during periods of time preceding convulsive seizures than during times that are seizure-free.
- To examine correlation of study drug dose and fever-induced convulsive seizure frequency, severity, and duration.
- To examine the timing of diary-reported events vs. automatically detected events.
- To assess quality of life while using the Embrace system with the following measures:
  - Quality of Life (QoL) of the parent/caregiver using the EQ-5D-5L scale.
  - Affective symptoms of the parent/caregiver using the Hospital Anxiety and Depression Scale (HADS).
- To assess caregiver stress using the Perceived Stress Scale (PSS).

### 3. INVESTIGATIONAL PLAN

#### 3.1 OVERALL STUDY DESIGN AND PLAN

This is a sub-study to the ZX008-1503 OLE study. All participants in this sub-study will have participated in Study ZX008-1501 or ZX008-1504 Cohort 2 in the United States or Canada and then continued in Study ZX008-1503, which is a multicenter, open-label, long-term safety study of ZX008 (fenfluramine hydrochloride) in pediatric and young adult subjects with Dravet syndrome. The main Study ZX008-1503 consists of a 12-month OLE Treatment Period and a 2-week Post-Dosing Period in which all subjects will receive ZX008 starting at 0.2 mg/kg, titrating to an effective dose, up to 0.8 mg/kg/day (not to exceed 30 mg/day). Thus, subjects who complete the main study will have been treated with ZX008 for a minimum of up to 1 year. This sub-study will include up to 20 participants who meet the entry criteria for the main Study ZX008-1503 and who are willing to wear the Embrace watch and their parent/caregiver who is willing to use the Embrace Alert app per the user instructions for 12 consecutive weeks. Those invited to participate will undergo all procedures included in the main Study ZX008-1503, plus any additional procedures for the sub-study. At the conclusion of the sub-study, participants will only use the ERT seizure diary for the remainder of their participation in the main Study ZX008-1503. Efficacy analyses for sub-study participants that rely on the ERT seizure diary or that are specific to the Embrace watch will not be included in the main ZX008-1503 analyses.

At the time of consent for the main Study ZX008-1503 subjects will also be presented with the consent for this sub-study. Subjects who consent to participate in the sub-study will be fitted with an Embrace watch at Study Visit 1. Subjects (and/or parents/caregivers) will also be given instructions on how to use the Embrace system. The Alert app must be running on the provided iPod touch and remain in close proximity of the patient. However, parents/caregivers will continue to use the ERT seizure diary to record the number/type of seizures, use of rescue medication, and study drug administration.

At pre-determined assessment times, parents/caregivers will complete questionnaires specific for the sub-study, including:

1. Ease of Use Questionnaire, which comprises a 5-point Likert scale (1- Very easy, to 5- Very difficult).
2. Perceived Stress Scale (PSS), which consists of 10 items.
3. Parents/caregivers will also complete the EQ-5D-5L and HADS in order to assess quality of life while using the Embrace.

A schedule of sub-study assessments is provided in Table 1.

**Table 1: Schedule of Additional Assessments for Subjects Enrolled in the Sub-study**

Study Assessments	Visit 1 a	OLE Treatment Period			
		Visit 2		Visits 3-4 (Months 1-2) b	Visit 5 (EOS/ET) Month 12 c
Study Day	1 a	15		30, 60	90
		Clinic	Phone		
Informed Consent	X				
Entry Criteria	X				
Issue/fit Embrace watch system and provide instructions on its use	X				
Perceived Stress Scale (PSS)	X			X	X
Ease of Use Questionnaire		X		X	X
EQ-5D-5L (QoL of parent/caregiver)	X			X	X
HADS (Affect of parent/caregiver)	X			X	X

Abbreviations: EOS/ET=End of Study/Early Termination; HADS=Hospital Anxiety and Depression Scale; OLE=open-label extension; PSS=Perceived Stress Scale; QoL=Quality of Life

Note: All other Study ZX008-1503 procedures must be completed as described in the main study protocol.

a Visit 1/Day 1 for sub-study ZX008-1503-SS01 corresponds to Visit 1/Day 1 for the main Study ZX008-1503.

b Subjects who continue for an additional 3 months will repeat Study Day 30 and 60 procedures on Study Days 90 and 120, and the end of study visit will be Study Day 150.

c At EOS/ET, subjects will be required to return the Embrace watch and study iPod.

